It is well known that interfascial plane blocks can result in systemic levels of LAs that achieve therapeutic concentrations (15) similar to that observed by intravenous infusions of LA (16,17). This is very likely the case for the ESP block, especially since the clinical and anatomical studies have conflicting findings regarding the loco-regional effects. Although intravenous lidocaine has shown some promise to prevent post-operative cognitive dysfunction (18,19), its effect on postoperative pain is not well studies. One study utilizing low dose lidocaine failed to show improvement in pain scores or opioid consumption, but the study did not utilize standardized multimodal analgesia

regimen (20). It is currently unknown whether the analgesic benefits of interfascial plane blocks are due to the multimodal analgesic regimen, the loco-regional benefits of the blocks, the systemic levels of local anesthetics following the block performance or a combination of all. We hypothesize that the mechanism by which the ESP block produces analgesia in the background of multimodal analgesia is probably related to the systemic absorption of local anesthetics. In addition, the safety of the ESP block using high doses of LA in cardiac surgery patients has not been rigorously assessed. We propose a pragmatic study to address both unknowns, the mechanism and safety of ESP following cardiac surgery.

III. Study Aims

- 1. The hypothesis of this study is that the analgesic effects of ESP can be attributed to its systemic distribution rather than its locoregional effects. A finding that lidocaine administered by ESP block achieves plasma concentrations in the analgesic range (2-5 ug/ml) at steady state will support our hypothesis whereas inability to reach analgesic levels will suggest that systemic distribution of local anesthetic is not a significant contributing factor of analgesia.
- 2. Despite the use of clinically acceptable doses, plasma concentrations of local anesthetic have been known to reach toxic levels following bilateral paravertebral blocks. This may also be true of ESP blocks. This study will address this concern and help establish a safety profile for ESP blocks in the cardiac patient population.

IV. Administrative Organization

University of Iowa Hospitals and Clinics—CVICU and Laboratories

V. Study Design

- i. Experimental design of the study (e.g., single-blind, double-blind): Randomized

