 - Anxiolytic medications. Minimal anxiolytic medications given before surgery including midazolam given by anesthesia provider.
 - B. Intra-Operative Phase (Standard of Care At discretion of Anesthesia Provider)
 - Intraoperative opioid administration. Fentanyl IV given as needed for pain but typically < 1 mg for procedure.
 - Hydromorphone 0.5 1 mg given near completion of procedure
 - Intraoperative multimodal analgesia. If time since preoperative acetaminophen dose significantly exceeds 6 hours, acetaminophen 1000 mg IV, or via NG route is considered
 - Postoperative sedation initiated. Near the end of the procedure, dexmedetomidine or propofol infusion is begun for postoperative sedation in ICU while intubated

• All patients will receive dual post-operative nausea and vomiting (PONV) prophylaxis in the form of ondansetron and dexamethasone at appropriate time periods.

If the surgical procedure takes longer than 12 hours, the subject will be withdrawn from the study.

C. Block Performance/Procedure

• Upon arrival to the CV-ICU, patients will be assessed for eligibility to extubate based on hemodynamic and pulmonary stability on a case-by-case basis with the aim to extubate as early as possible. When appropriate, extubation will proceed following the CV-ICU Fast Track Extubation protocol that is already in place. Extubation is not required prior to the administration of study drug via IV or ESP catheters route. Participation in the study can proceed as long as after assessment by clinicians, the subject is extubated or ready to be extubated.

[figure not shown]
D. Group ESP (Study Procedures)

- Bilateral ultrasound guided erector spinae plane (ESP) catheters will be inserted either pre- or post-operatively.
- After confirming that there are no contra-indications, the subject will receive lidocaine via ESP catheter.
- Patients will receive lidocaine at a dose of 2 mg/kg ideal body weight (IBW) as bolus divided equally between the two ESP catheters.
- Subjects will then lie in a supine position.
- Lidocaine infusion via ESP catheters either through 2 dedicated pumps or via a single pump and a y-connector at a rate of 2 mg/kg/hour for approximately 48 hours.
- Blood samples will be drawn at 5, 30, 60, 120 minutes, 6 and 24 hours and assessed for lidocaine concentration.

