- Pain scores (resting and with movement/cough) will be collected from bedside record and EPIC medical record. Standard assessment protocol already in place has this charted every 2 4 hours by ICU nursing staff.
- All patients will receive continued oral multimodal analgesia
- When not eligible to receive oral medications (e.g. NPO), pain analgesia will be provided through an IV route. This can include an IV PCA pump using hydromorphone 0.2 mg with a lockout of 10 minutes and a maximum dose of 6 mg in 4 hours continued postoperatively.
- If oral medications are insufficient to provide pain relief, and the subjects are not receiving medications via PCA, pain medications

will be provided IV. • Opioid doses (both oral and IV) will be assessed and reported in morphine equivalents.

E. Group IV (Study Procedures)

- Patients will receive lidocaine at a dose of 2 mg/kg ideal body weight (IBW) through IV route.
- Subjects will then lie in a supine position.
- Lidocaine infusion via IV route at a rate of 2 mg/kg/hour for approximately 48 hours.
- Blood samples will be drawn at 5, 30, 60, 120 minutes, 6 and 24 hours and assessed for lidocaine concentration.
 - Pain scores (resting and with movement/cough) will be collected from bedside record and EPIC medical record. Standard assessment protocol already in place has this charted every 2 4 hours by ICU nursing staff
 - All patients will receive continued oral multimodal analgesia
- When not eligible to receive oral medications (e.g. NPO), pain analgesia will be provided through an IV route. This can include an IV PCA pump using hydromorphone 0.2 mg with a lockout of 10 minutes and a maximum dose of 6 mg in 4 hours continued postoperatively.
- If oral medications are insufficient to provide pain relief, and the subjects are not receiving medications via PCA, pain medications will be provided IV.
- Opioid doses (both oral and IV) will be assessed and reported in morphine equivalents.
- ii. Provide a schedule of all study assessments and subject activities, including a tabular representation or timeline as applicable

VII. Safety Monitoring Plan

i. Definition of adverse events, serious adverse events:

An adverse event (also referred to as an adverse experience) can be any unfavorable and unintended sign (e.g., an abnormal laboratory finding), symptom, or disease temporarily associated with the use of a drug, without any judgment about causality or relationship to the drug.

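### With the same nominal lidocaine dose in both arms, an ESP steady-state level of 2-5 ug/ml is largely a result of dose and clearance and cannot show that ESP analgesia is systemic

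*Combined protocol and SAP*

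**What the plan says.** Section VI.d.i gives the two arms the same nominal dosing.

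- **ESP bolus (D, Group ESP):** "Patients will receive lidocaine at a dose of 2 mg/kg ideal body weight (IBW) as bolus divided equally between the two ESP catheters".
- **IV bolus (E, Group IV):** "Patients will receive lidocaine at a dose of 2 mg/kg ideal body weight (IBW) through IV route".
- **ESP infusion:** "Lidocaine infusion via ESP catheters either through 2 dedicated pumps or via a single pump and a y-connector at a rate of 2 mg/kg/hour", for about 48 hours.
- **IV infusion:** "Lidocaine infusion via IV route at a rate of 2 mg/kg/hour for approximately 48 hours".

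Both arms have the same sampling times: "Blood samples will be drawn at 5, 30, 60, 120 minutes, 6 and 24 hours and assessed for lidocaine concentration". No concentration sample is scheduled between 24 h and the end of the infusion.

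Section III, Aim 1, states how mechanism will be read. On one side, evidence that "lidocaine administered by ESP block achieves plasma concentrations in the analgesic range (2-5 ug/ml) at steady state will support our hypothesis". The other branch, for an ESP level that stays below that range, reads: "inability to reach analgesic levels will suggest that systemic distribution of local anesthetic is not a significant contributing factor of analgesia". This rule uses only the ESP level. It draws on neither the IV arm nor the pain and opioid data, which section V lists as separate outcomes. Section VIII applies equivalence tests to primary outcome measures that it does not name, and it gives no margin.

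**The concern.** When drug is infused at a constant rate into a tissue plane and all of it is absorbed, it enters the circulation at that same rate once steady state is reached. Route affects how quickly the plateau comes, not its expected height. Aim 1 places its decision at the plateau, the point where route matters least. Where the drug relieves pain does not enter the calculation, so a block that worked wholly locally and one that worked wholly systemically would produce the same plasma level.

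At stake is the trial's main scientific conclusion. Followed as written, Aim 1 could report support for systemic action when the result mostly reflects the chosen dose and the patients' clearance.

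**Working it through.** **Inputs from the protocol.** Bolus 2 mg/kg and infusion 2 mg/kg/h in both arms (VI.d.i.D and E); target range 2-5 ug/ml, which is 2-5 mg/L (III, Aim 1); sampling at 5, 30, 60 and 120 min, 6 h and 24 h. The protocol gives no clearance, volume, absorption rate or fraction absorbed, so those below are assumptions shown as ranges. It derives no plasma level of its own that could be reproduced first.

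**Step 1: steady state.** Css = F × R / CL, where F is the fraction absorbed, R the infusion rate and CL the clearance. With F = 1 and R = 2 mg/kg/h (33.3 ug/kg/min):

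- Css = 5 mg/L when CL = 2/5 = 0.40 L/h/kg (6.7 mL/min/kg).
- Css = 2 mg/L when CL = 2/2 = 1.0 L/h/kg (16.7 mL/min/kg).

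Between those clearances the level is in range by either route. Examples:

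| CL (mL/min/kg) | Css = 33.3/CL (ug/ml) | Relative to 2-5 |
|---|---|---|
| 5 | 6.67 | above |
| 8 | 4.17 | in |
| 10 | 3.33 | in |
| 12 | 2.78 | in |
| 20 | 1.67 | below |

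**Step 2: incomplete absorption.** F scales the ESP level. With F = 0.8 the clearance window becomes 0.8 × 6.7 to 0.8 × 16.7, or 5.3-13.3 mL/min/kg. The ESP/IV ratio at steady state is then 0.8, which measures delivery and absorption, not mechanism.

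**Step 3: approach to steady state.** One-compartment model with the stated bolus and infusion; IV input direct, ESP input by complete first-order absorption. Assumed clearance 0.4-1.0 L/h/kg, volume 1.0-1.5 L/kg, absorption half-life 0.25-4 h. ESP/IV concentration ratio:

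| Time | Ratio |
|---|---|
| 5 min | 0.01-0.21 |
| 30 min | 0.07-0.75 |
| 60 min | 0.13-0.94 |
| 2 h | 0.23-1.00 |
| 6 h | 0.52-1.00 |
| 24 h | 0.97-1.00 |

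**Step 4: sensitivity of the 24 h ratio.** With an absorption half-life of 8 h in the same model it falls to about 0.83 at the lowest. With elimination half-lives of 1.5-5 h instead, it is 0.93-1.00 for absorption half-lives up to 4 h and 0.77-0.86 for 8 h. In that 8 h case it recovers to 0.96-0.98 by 48 h, a time that is not sampled.

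**Step 5: the two-pump wording.** If 2 mg/kg/h were delivered by each of two pumps, the ESP input would be 4 mg/kg/h and its steady-state level would double (at 10 mL/min/kg, 6.67 against 3.33 ug/ml). The arms would then differ, but because of dose.

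**The case against.** The strongest reply is that equal dosing is a strength. It matches systemic exposure, so a difference in pain or opioid use at matched levels would point to a local effect. That stands: the fault lies in the inference drawn in Aim 1, not in the matched doses.

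A second reply is that Aim 1 keeps some value as a check of a necessary condition, because a sub-analgesic level weakens a systemic explanation. That also stands. But high clearance, incomplete or slow absorption, or sampling before steady state could each produce a low level, and none of these demonstrates local action.

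Several stronger readings are tempting, and the protocol does not support them.

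- **That the Aim 1 result is fixed in advance.** It is not. The clearance range assumed in Step 3 is exactly the one that yields 2-5 ug/ml. The protocol states no clearance, and 5 or 20 mL/min/kg would fall outside the range.
- **That PK equivalence at 24 h is a certain finding.** No section specifies such a test. Nor does a true ratio of 1 guarantee success: assuming 35 per arm, limits of 0.80-1.25, log-scale two one-sided tests at 0.05 each and no dropout, power is about 87% at a between-patient CV of 30%, 55% at 40% and 25% at 50%.
- **That the early samples serve no purpose.** Early and peak levels bear on the toxicity question in Aim 2.
- **That mechanism should instead be read from pain at 2 h and 6 h, while levels may differ.** That would confound route with systemic exposure. Pain is charted only every 2-4 h, and VI.d.i.C allows study drug to start before extubation, so early scores may be sparse or affected by sedation.

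**Conclusion.** The concern holds for the inference in Aim 1. An ESP level of 2-5 ug/ml at steady state is what the nominal dose produces for any clearance of 0.40-1.0 L/h/kg when absorption is near complete, so it does not separate systemic from local analgesia. A comparison of ESP and IV levels at 24 h would not repair this. Its expected ratio is about 0.97-1.00 for absorption half-lives up to 4 h and about 0.83 at the lowest for 8 h (0.77 with the longer elimination half-lives), so it would mainly check delivery and absorption.

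The Step 1 window needs only mass balance, steady state, near-complete absorption and a total ESP rate of 2 mg/kg/h. The 24 h ratios rest in addition on the one-compartment model and the assumed ranges. The conclusion does not extend to the early samples, to Aim 2 or to the between-arm comparison of analgesia.

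**What to change.** **Section III, Aim 1.** Stop treating an in-range ESP level as support for the systemic hypothesis, and state that a low level weakens a systemic explanation without demonstrating local action. Base the mechanism conclusion on the randomised ESP-versus-IV comparison of pain scores and opioid use, over the period when plasma levels are expected to match (around 24 h and later, within the 48 h infusion).

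**Section VIII.** Name that comparison and pre-specify its equivalence margin and time window. Report 24 h concentrations as a check of delivery and absorption. Report AUC 0-6 h and the highest observed level as descriptive PK and safety data for Aim 2.

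**Section VI.d.i.** Reconcile the ESP infusion wording on whether the stated rate is the total or per pump, because matched exposure depends on it. The bolus lines specify ideal body weight and the infusion lines do not; reconcile these too.

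**Cost.** Rewording only: no new samples or assessments and no change to doses. The price is scientific. The plasma level alone can no longer be claimed as support for the hypothesis, and the mechanism conclusion will rest on noisier pain and opioid data. With no sample after 24 h, matching beyond that point is inferred, not observed.

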An adverse event or suspected adverse reaction is considered "serious" if, in the view of either the investigator or sponsor, it results in any of the following outcomes: Death, a life-threatening adverse event, inpatient hospitalization or prolongation of existing hospitalization, a persistent or significant incapacity or substantial disruption of the ability to conduct normal life functions, or a congenital anomaly/birth defect.

Any adverse experience that places the subject, in the view of the investigator, at immediate risk of death from the reaction as it occurred, or it is suspected that the use or continued use of the product would result in the patient's death.

ii. What procedures will be used to monitor subject safety?

Careful and constant monitoring of cardiovascular and respiratory (adequacy of ventilation) vital signs and the patient's state of consciousness should be accomplished. It should be kept in mind at such times that restlessness, anxiety, tinnitus, dizziness, blurred vision, tremors, depression or drowsiness may be early warning signs of central nervous system toxicity.

For the purpose of being prepared to deal with the side effects of lidocaine (Bradyarrhythmia, hypotension, infusion site reactions), the blocks will only be performed in the Cardiac ICU, where pharmacological and non-pharmacological measures are available to treat these side effects. The foundation of local anesthetic toxicity is outlined in seizure management with pharmacological seizure management, advanced cardiac life support (ACLS) to support the heart and use of 20% lipid emulsion to reverse local anesthetic toxicity. Oxygen can be provided for patients needing improved oxygenation and all the emergency medications, pharmacists and intensivists are readily available in the ICU.

- iii. Who (list names) will identify, document, and report adverse events? Nursing staff in the CVICU should report adverse events to [name] or [name] within 12 hours of the event. After the subject is stabilized this information will be reported to a member of Anesthesia Innovative Research Core who will report the event to the IRB.
- iv. What is the frequency for review of summarized safety information and who will perform the review (e.g., safety monitoring board)?

No committee is currently in place for this pilot study.

v. What are the stopping rules with regard to efficacy and safety?

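### Adverse events are tied to drug use and reported only from the CVICU, so ESP catheter harms before dosing, or in patients never dosed, have no assured place in the safety data

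*Combined protocol and SAP*

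**What the plan says.** **Definition.** Section VII.i counts an unfavourable and unintended sign, "symptom, or disease temporarily associated with the use of a drug, without any judgment about causality or relationship to the drug". (The adverb is probably a slip for temporally.) The further wording on risk of death is also tied to a product: "it is suspected that the use or continued use of the product would result in the patient's death". Neither mentions a procedure or a catheter.

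**Expected harms.** Section VII.ii lists the "side effects of lidocaine (Bradyarrhythmia, hypotension, infusion site reactions"). Only the last of these is local.

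**Reporters.** Section VII.iii names CVICU nursing staff. Nobody is named for the pre-operative area or the operating room.

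**Insertion.** Section VI.d, Group ESP: "Bilateral ultrasound guided erector spinae plane (ESP) catheters will be inserted either pre- or post-operatively". Study lidocaine comes later, after a check for contraindications.

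**Leaving before dosing.** Section VI.d, Intra-Operative Phase: "If the surgical procedure takes longer than 12 hours, the subject will be withdrawn from the study". Under Block Performance, taking part also depends on the patient being extubated or ready for it.

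**Safety objective.** The abstract says that the study will evaluate the safety of ESP blocks as well as their analgesic efficacy. Section III, item 2, notes that "plasma concentrations of local anesthetic have been known to reach toxic levels following bilateral paravertebral blocks" and continues: "This study will address this concern and help establish a safety profile for ESP blocks in the cardiac patient population".

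No section states when event collection starts, who belongs to the safety set, or how safety data will be tabulated.

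**The concern.** Both arms receive lidocaine, but only ESP patients have two catheters inserted. An event definition that starts from a drug, with reporters in one unit only, fits harms of lidocaine during the infusion. It does not clearly fit harms of the needle or catheter, least of all when insertion takes place before surgery in another part of the hospital.

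The stake is the comparison of safety between routes. Harms of insertion can occur in one arm only, so if some are not recorded the error has one direction: ESP looks safer than it was. With an arm of about 35 patients, few such events can be expected, and each carries weight in any statement about the safety of the block.

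**Working it through.** This is mainly a question of wording, so the first step is to follow an insertion harm through the rules as written.

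1. *Catheter placed in the CVICU, patient dosed.* The named reporters are present. A harm still there once lidocaine starts meets the definition, because no causal judgment is required.
2. *Catheter placed before surgery, patient dosed, harm still present or found during the infusion.* It counts, for the same reason.
3. *Catheter placed before surgery, patient dosed, harm resolved or never written down before the first dose.* On the natural reading of the drug as study lidocaine, it precedes drug use. No reporter is named for that period, and no start of collection reaches back to it. It is not assured a place.
4. *Catheter placed, patient never dosed.* Section VI.d gives three routes: surgery beyond the 12-hour limit, a contraindication found after insertion, or a patient neither extubated nor ready to be. There is no study-drug use to attach the event to, and no safety set that keeps the patient. It is not assured a place.

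The gap is therefore paths 3 and 4. Neither has a counterpart in the IV arm for catheter harms.

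**Scale.** The only design figure is a total of 70 patients (Section V.iii). No margin, standard deviation or power is given, so that figure cannot be reproduced; the point does not depend on it. The allocation ratio is not stated. Assuming 1:1, 70 / 2 = 35 ESP patients.

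- Zero events in 35, one-sided 95% upper limit: 1 − 0.05^(1/35) = 0.082, or 8.2%.
- Zero events in 35, upper end of a two-sided 95% interval: 1 − 0.025^(1/35) = 0.100, or 10.0%.
- One event in 35 (1/35 = 2.9%), one-sided 95% upper limit: solve (1 − U)^35 + 35U(1 − U)^34 = 0.05. At U = 0.1285 the terms are 0.0081 + 0.0419 = 0.0500, so U is 12.9%.
- Chance of at least one insertion harm in 35, 1 − (1 − p)^35: 30%, 51% and 83% at assumed true rates p of 1%, 2% and 5%.
- If 2 or 5 ESP patients were never dosed and dropped from the count (assumed), the zero-event limit would be 1 − 0.05^(1/33) = 8.7% or 1 − 0.05^(1/30) = 9.5%.

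Losing a few patients from the denominator changes little. Losing one event from the numerator changes the reported result from one in 35 to none, and the upper limit from 12.9% to 8.2%.

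**The case against.** The strongest reply is that the gap is narrow. The definition says a drug, not the study drug, and every patient receives gabapentin and acetaminophen before surgery. Read literally, it could already cover the time of insertion. It asks for no causal link, so an injury present or found during the roughly 48-hour infusion would count. Section III, item 2, starts from toxic plasma levels and says only that the study will help establish a profile; it makes no express undertaking about insertion harms. These points stand, and they confine the concern to paths 3 and 4. They do not close it. The literal reading is not the natural one, and it supplies neither a reporter nor a safety set.

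A reader might also infer more than the documents support:

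- *That every insertion harm is excluded, or that an undosed patient yields no event at all.* The text says that such a patient is withdrawn and is silent on safety follow-up.
- *That the protocol itself raises hematoma as a risk of ESP.* Section II attaches that concern to epidural, intrathecal and paravertebral blocks, and contrasts ESP as superficial and non-neuraxial.
- *That insertion comes up to 12 hours before lidocaine.* Twelve hours is a cap on the length of surgery; the interval from insertion to dose is not given.
- *That insertion harms are the only ones that differ by route.* Systemic exposure may differ too and is measured, infusion site reactions are listed, and unintended subarachnoid injection is addressed in Section VI.c.
- *That the number of patients observed for insertion harm is halved.* That would require assumptions about the share of pre-operative insertions and the loss of every harm among them, which the documents do not support.

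**Conclusion.** The point holds in its limited form and should be corrected. The definition does not expressly cover harms of the ESP procedure or catheter. The plan also lacks a start of collection, a reporter outside the CVICU and a safety set that would secure those harms when they precede dosing or occur in patients never dosed. Any loss favours ESP.

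Its size cannot be estimated, because the documents give neither the share of catheters placed before surgery, nor the rate of insertion harm, nor the number likely to go undosed. The 8.2% and 10.0% limits assume 1:1 allocation and full capture of events. They would apply to zero events in 35 whatever the definition, so they show how little room there is for a missed event; they do not measure bias. The conclusion rests on reading the drug as study lidocaine. If the sponsor intends the wider reading, the text still needs to say so.

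A related inconsistency adds to the doubt. Section VII.ii says that blocks are carried out solely in the Cardiac ICU, while Section VI.d permits catheter insertion before surgery. The two agree only if block means the lidocaine injection and not the placement of the catheter.

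**What to change.** - **Definition.** Extend Section VII.i to events associated with study drug or with attempted insertion, presence or removal of an ESP catheter.
- **Window.** Collect events in both arms over the same period, from one common pre-operative time point, no later than the first needle pass, to the end of infusion or catheter removal, whether or not the patient is dosed. A common window keeps undosed IV patients under observation too. It also avoids a new bias against ESP from recording intra-operative events in one arm only.
- **Reporter.** Name a role responsible for the pre-operative and operating-room period.
- **Safety set and table.** Keep every patient with an attempted catheter in the safety set, dosed or not. Tabulate procedure and catheter events separately from lidocaine events, with exact 95% limits.
- **Consistency.** Reconcile Section VII.ii with Section VI.d on where and when blocks and catheters are placed.

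The cost is one amended definition, a stated window, a named reporter, a case-report field and a table. More events will be recorded, mainly in the ESP arm. Because Section VII.v pauses the study when an adverse event occurs, there may be more pauses, and the study team should plan for that.
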